2.2 Secondary Clinical Objectives

- 2.2.1 To evaluate the impact of initial treatment on median OS and Hazard Ratio for death.
- 2.2.2 To determine whether initial treatment choice significantly improves 3 year OS.
- 2.2.3 To evaluate the anti-tumor activities (RECIST-defined response rate, median PFS) and safety profiles of ipilimumab + nivolumab and dabrafenib-trametinib in a Cooperative Group trial of patients with V600 mutant melanoma.
- 2.2.4 To evaluate the activity (RECIST-defined response rate, median PFS) and safety of dabrafenib + trametinib in patients who have had disease progression on ipilimumab + nivolumab and in comparison to its activity and safety in ipilimumab + nivolumab naïve patients.
- 2.2.5 To evaluate the activity of ipilimumab + nivolumab (RECIST-defined response rate, median PFS) and safety in patients who have had disease progression on dabrafenib + trametinib and in comparison to its activity and safety in dabrafenib + trametinib naïve patients.
- 2.2.6 To assess the feasibility of crossover to the alternative treatment strategy (percentage of patients who are able to cross-over from one arm to the other and complete at least an initial course (12 weeks) of treatment after crossover without intervening symptomatic disease progression or treatment limiting toxicity).

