4.2 Randomization (Step 2)

Patients on Arm A or Arm B will re-register and crossover to Step 2. Arm A patients will re-register and crossover to Arm C in Step 2. Arm B patients will re-register and crossover to Arm D in Step 2.

NOTE: Before crossover to Arm C, Arm A patients must have melanoma that is metastatic and clearly progressive on Step 1 therapy. Confirmation of PD with second imaging scan after 4 weeks is not needed in patients with symptoms or laboratory data (rising LDH) supporting disease progression.

NOTE: In response to the Data and Safety Monitoring Committee (DSMC) recommendations, Arm B patients may cross over to Arm D either prior to or at disease progression.

Treatment must start within 7 working days of registration to Step 2.

Rev. Add13

Rev. 12/15

Rev. Add10	4.2.1	Protocol Number Investigator Identification 
 • Institution and affiliate name • Investigator's name
	4.2.2	Patient Identification 
 • Patient's initials (first and last) • Patient demographics 
 • Sex • Birth date (mm/yyyy) • Race • Ethnicity • ZIP code • Method of payment • Country of residence
	4.2.3	Eligibility Verification Patients must meet all of the eligibility requirements listed in Section 3.2 .
	4.3	Additional Requirements
	4.3.1	Patients must provide a signed and dated, written informed consent form. NOTE: Copies of the consent are not collected by the ECOG-ACRIN Operations Office – Boston.
	4.3.2	Pathological samples are required to be submitted for central diagnostic review (mandatory) and for defined laboratory research studies (per patient consent) as indicated in Section 10 .
Rev. 5/17	4.3.3	Biological samples are to be submitted for defined laboratory research studies per patient consent as outlined in Section 10 .

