Progressive disease will be determined by RECIST criteria for all arms. Crossover should occur at a minimum of 1 week after defined PD on either arm. Patients on either arm with “equivocal” progression, defined as PD by RECIST in the absence of disease related symptoms and in the setting of evidence of potential ongoing treatment benefit (e.g. falling LDH, shrinkage of the majority of lesions) can delay cessation of initial treatment and crossover until PD is confirmed with a repeat scan performed 4 weeks (+/- 1 week) after the initial scan. If RECIST PD is confirmed then treatment discontinuation must happen at that time. The initial PD scan will be designated the time of PD. For patients on Step 1, a washout period of 1 week is still required from either the last dose of dabrafenib/trametinib or the first missed dose of nivo +/- ipi due to documentation of PD prior to crossover. Potential exceptions to this 1 week washout must be discussed with study PI and approved. Crossover should happen within 12 weeks of initial date of RECIST defined PD. Exceptions to this timeframe must be discussed with the study PI. If PD is not confirmed, (e.g. new lesions no longer present or are getting smaller, or overall disease is smaller and no longer meets criteria for RECIST defined PD) patient may continue on therapy with scans performed at the time dictated by the protocol e.g. subsequent scans should continue at the 12 week interval defined from the time of treatment initiation for that step of therapy. The same rules will apply to discontinuation of study treatment after crossover to the alternative treatment regimen.

Patients taken off treatment for any reason other than progression per RECIST criteria will undergo tumor imaging at protocol defined times and cannot proceed to Step 2 until RECIST defined disease progression is documented (more frequent scanning is allowed in this situation). Patients taken off treatment on Arm B can proceed to Arm D without the need for documented progression.

Patients must meet Step 2 eligibility criteria at the time of crossover registration with improvement of treatment related toxicity to grade 1 or less. Some notable exceptions are below. Please see Section [3.2](#) for more details.

1. Patients on Arm A may be on a stable (for at least 1 week) or tapering dose of steroids at time of crossover to dabrafenib and

trametinib. Patients on Arm B must be off of steroids for at least 2 weeks at time of crossover.

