6.1.4.4 Evaluation of Best Overall Response

The best overall response is the best response recorded from the start of the treatment until disease progression/recurrence or non-protocol therapy (taking as reference for progressive disease the smallest measurements recorded since the treatment started). The patient's best response assignment will depend on the achievement of both measurement and confirmation criteria.

For Patients with Measurable Disease (i.e., Target Disease)

Target Lesions	Non-Target Lesions	New Lesions*	Best Overall Response	Remarks
CR	CR	No	CR	****
CR	Non-CR/Non-PD***	No	PR	****
CR	Not evaluated	No	PR	
PR	Non-PD***/not evaluated	No	PR	
SD	Non-PD***/not evaluated	No	SD	Documented at least once ≥ 24 wks from study entry
PD	Any	Yes or No	PD	No prior SD, PR or CR
Any	PD**	Yes or No	PD***	
Any	Any	Yes	PD	

* See RECIST 1.1 manuscript for further details on what is evidence of a new lesion.
 
** In exceptional circumstances, unequivocal progression in non-target lesions may be accepted as disease progression.
 
*** PD in non-target lesions should not normally trump target lesion status. It must be representative of overall disease status change, not a single lesion increase. Please refer to the Evaluation of Non-Target Lesions – Progressive Disease section for further explanation.
 
**** To be assigned a status of partial or complete response, changes in tumor measurements must be confirmed by a repeat assessment performed no less than six weeks after the criteria for response is met.
 
NOTE: Patients with a global deterioration of health status requiring discontinuation of treatment without objective evidence of disease progression at that time should be reported as “symptomatic deterioration.” Every effort should be made to document the objective progression even after discontinuation of treatment.
				

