Response rate and PFS for patients who are treated with Ipilimumab/Nivolumab before crossover (arm A) vs. for patients who were initially treated with dabrafenib/trametinib and crossed over to Ipilimumab/Nivolumab will be compared (arm D). For the latter group, PFS will be defined as the time from cross-over until progression or deaths without progression. Tumor response will be assessed from the start of a particular therapy and baseline will be recalculated at time of cross over therapy. Patients without RECIST defined measurable disease at time of crossover will be excluded from the response assessment. Response rates will be compared using the Fisher's exact test and PFS will be compared using the log-rank test. Safety profile of these two groups will also be compared using the Chi-square or Fisher's exact test. Analyses specified in this paragraph will be repeated for arms B vs. C comparison.

Toxicity rate for individual AEs, categorized AEs and worst degree AEs will be compared in arms A vs. B and in arms C vs. D using the Chi-square or Fisher's exact test. Two-sided p-values will be reported for these comparisons.

In the event of missing data, it will be assumed that the data will be missing at random and no imputation will be performed.

Subset analyses are planned for all stratification factors (ECOG PS, LDH) and well known prognostic factors such as age, sex, ulceration, etc. Subset analyses are considered to be exploratory in nature.

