The above health states are progressive, but it is not required for all patients to go through all the 5 states. For example, for patients without disease progression on the initial treatment, they will not enter TOX2, TWiST2, and PROG states.

The Q-TWiST score is obtained by summing the weighted clinical health state durations. The Q-TWiST score for each treatment arm will be calculated using the following formula:

$$Q-TWiST = (u_{TOX1} \times TOX1) + (u_{TWiST1} \times TWiST1) + (u_{TOX2} \times TOX2) + (u_{TWiST2} \times TWiST2) + (u_{PROG} \times PROG)$$

where u_{TOX1} , u_{TWiST1} , u_{TOX2} , u_{TWiST2} , u_{PROG} represent the average group utility weight for each health state for that arm; TOX1, TWiST1, TOX2, TWiST2, and PROG represent the mean duration of the health state of that arm.

In the Q-TWiST analysis, each health state is assigned a weight ranging from 0 (representing death) to 1 (indicating perfect health). These weights are called utility scores as well. For each patient, EQ-5D will be administered multiple times (at baseline, at each cycle while during the initial and subsequent treatment period, then every 3 months up to 2 years from study entry if patients are off protocol

treatment and not receiving non-protocol therapy, at end of treatment in each step (before and after crossover), and at dose modification) and its score will be used to derive the utility score. In this study, the utility score is conditional on the patient-reported health state on the 5 dimensions (mobility, self-care, usual activities, pain/discomfort, anxiety/depression) captured in EQ-5D. A number ranging from 1 to 5 will be assigned to each level in each of the 5 dimensions. A patient's health state thus can be labeled using a 5-number descriptor ranging from 11111 to 55555. A utility score corresponding to each possible descriptor elicited from general population samples (by country) was provided in the file "EQ-5D-5L_Crosswalk value sets" posted in the website of www.euroqol.org.⁴⁶ We are going to use the value set elicited from US subjects for our patients in this study. For instance, a health state with a descriptor of "11111" is given a utility score of 1.000, "12111" is assigned a utility value of 0.854, and "43333" is with a utility score of 0.573.

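### Sections 9.4 and 9.8 still assume that progression precedes crossover, although Arm B alone may now enter Arm D before progression; this leaves Arm D response and PFS, Arm B PFS and Q-TWiST without a rule for early switchers

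*Combined protocol and SAP*

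**What the plan says.** **Crossover rule.** Section 4.2 states that "Arm B patients may cross over to Arm D either prior to or at disease progression". The crossover rules after the Arm D regimen in Section 5.1 add: "Patients taken off treatment on Arm B can proceed to Arm D without the need for documented progression". The Arm A rule is unchanged: "Before crossover to Arm C, Arm A patients must have melanoma that is metastatic and clearly progressive on Step 1 therapy".

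**Objective.** Objective 2.2.5 asks about ipilimumab/nivolumab "in patients who have had disease progression on dabrafenib + trametinib", compared with its activity in patients not yet exposed to dabrafenib/trametinib.

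**Arm D analysis.** Section 9.4 compares Arm A with results "for patients who were initially treated with dabrafenib/trametinib and crossed over to Ipilimumab/Nivolumab will be compared (arm D", with PFS restarted at crossover. The same analyses are repeated for Arms B and C.

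**PFS from randomization.** In Section 9.2 the event is progression or death. Patients without an event are censored at their last progression-free assessment. Crossover is neither an event nor a censoring point.

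**Response.** Section 9.4 assesses response from the start of each therapy, with a new baseline at crossover. Section 6.1.4.4 gives the best-response window as "from the start of the treatment until disease progression/recurrence or non-protocol therapy".

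**Q-TWiST.** Section 9.8.2 ties TOX1 and TWiST1 to Step 1. TOX2 and TWiST2 start after progression on the initial treatment. It adds that "for patients without disease progression on the initial treatment, they will not enter TOX2, TWiST2, and PROG states".

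**The concern.** Patients who switch while progression-free can occur in only one randomized arm, and the analysis sections have no rule for them. Section 5.9.1 likewise still describes the second-treatment baseline as following progression and washout.

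Three results are exposed:

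- the answer to objective 2.2.5 (Arm D after dabrafenib/trametinib progression);
- the comparisons of dabrafenib/trametinib as initial therapy, that is A vs B (2.2.3) and B vs C (2.2.4);
- Q-TWiST, the primary PRO endpoint.

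If the rules stay open, they may be settled after the outcomes are known.

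**Working it through.** The plan gives no figure for early crossover. The nearest stated figure is the Q-TWiST power (Section 9.8.1): 135 per arm, difference 2.4 months, SD 7. Here 2.4 / (7 × √(2/135)) − 1.96 = 0.86, so power is 80.4% against the stated 80%. It reproduces, but it does not bear on how states and endpoints are defined.

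**1. Arm D as a mixture.** The inputs are illustrative:

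- 23% response after BRAF-inhibitor progression (Section 1.4: 6 of 26 patients, nivolumab alone);
- 42% (updated concurrent cohort) and 53% (32 patients at the top dose levels) for ipilimumab/nivolumab (Section 1.5);
- f, the assumed share of early switchers among Arm D patients evaluable for response.

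Pooled rate = 0.23 + f × (p − 0.23), with p = 0.42 or 0.53.

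| f | p = 0.42 | p = 0.53 |
|---|---|---|
| 0 | 23% | 23% |
| 20% | 27% | 29% |
| 40% | 31% | 35% |
| 60% | 34% | 41% |

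The contrast shrinks with it. Take 150 Arm A patients at 53% and 100 in Arm D (the first- and second-line numbers in Section 11.3), with early switchers also at 53%. Power for the response difference is 99.9%, 94.7%, 64.6% and 21.2% at f = 0, 25%, 50% and 75% (normal approximation, uncorrected).

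**2. Arm B PFS from randomization.** Take an exponential with median 9.4 months (Section 1.8), so λ = ln 2 / 9.4. Then S(6) = 64.2% and S(12) = 41.3%. Assume that a share s of event-free patients switches at month 6 and then has hazard hλ.

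As written: S(12) = S(6) × [(1 − s)e^(−6λ) + s e^(−6λh)]. If the switch counted as an event: S(6) × (1 − s)e^(−6λ).

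| s | As written, h = 0.5 | As written, h = 1 | As written, h = 1.5 | Switch counted as event |
|---|---|---|---|---|
| 10% | 42.3% | 41.3% | 40.5% | 37.1% |
| 25% | 43.8% | 41.3% | 39.2% | 31.0% |
| 50% | 46.4% | 41.3% | 37.2% | 20.6% |

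Censoring at the switch gives 41.3% throughout, if the censoring is non-informative. The written definition moves either way with h. The choice of rule can matter more than h.

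**3. Q-TWiST, following an early switcher through Section 9.8.2.**

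- *Toxicity.* Grade 3-4 days on Arm D are not in TOX1, which covers Step 1, nor in TOX2, which needs earlier progression on the initial treatment.
- *Time.* PFS1 is censored at the last Step 1 evaluation. The patient is kept out of TWiST2, yet PFS2 follows every Step 2 enrollee and so counts this time.
- *Utilities.* EQ-5D visits are assigned by absence of progression on initial treatment, with no Step 1 limit. Visits on Arm D therefore enter the TOX1 and TWiST1 averages.
- *After progression on Arm D.* Read literally, the sentence on state entry also keeps this patient out of PROG.

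**The case against.** Several stronger conclusions are tempting, and the documents do not support them.

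- *That the plan treats crossover as progression.* It does not. Section 9.2 makes crossover neither an event nor a censoring point. If it were progression, Arm B PFS would stop there and could carry no Arm D time.
- *That Arm D no longer measures activity after dabrafenib/trametinib failure.* It is a mixture, and the progressed subset can still be analysed.
- *That Arm D responses are credited to Arm B.* Section 9.4 assesses response per therapy with a new baseline. What remains is that it does not say when the Step 1 window ends, and Section 6.1.4.4 ends it only at progression or non-protocol therapy. Arm D is protocol therapy, so the two sections need reconciling.
- *That Arm B Q-TWiST wrongly absorbs ipilimumab/nivolumab time.* Including subsequent treatment is the purpose of the five-state design, and PFS1 stops at the last Step 1 evaluation. Absorption into first-line quantities is real only for the utilities.
- *That Arm B PFS is biased upward.* The direction depends on the hazard after the switch, as the table shows.

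It can also fairly be said that PFS regardless of switching is a legitimate treatment-policy estimand, and that censoring at the switch may be informative. Both points stand and shape the fix. Neither supplies the missing rules.

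**Conclusion.** The point holds for secondary and PRO analyses. Followed as written, Section 9.4 gives a mixed answer to objective 2.2.5. Arm B PFS includes second-line time in one arm only, without saying that this is intended. Q-TWiST has no consistent place for early switchers.

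The sizes are illustrations. The documents do not give the share switching early. The 23% is for nivolumab alone. Nothing shows that first-line response rates apply to patients leaving dabrafenib/trametinib before progression, who are re-baselined after possible shrinkage. The PFS figures rest on an exponential curve, a single switch time and an assumed later hazard.

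A reader might infer that the primary result is at risk. It is not: 2-year OS is analysed by randomized arm in all randomized patients, and its definition does not depend on crossover. The change should be made, but the trial's main conclusion does not hang on it.

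**What to change.** 1. **Objective 2.2.5.** Base the A-vs-D comparison on Step 2 registrants with RECIST progression on Step 1. Report early switchers separately.
2. **PFS.** Keep the Section 9.2 definition and label it the treatment-policy analysis. For the initial-therapy question (2.2.3) and the B-vs-C comparison (2.2.4), add an analysis that uses only assessments before Step 2 treatment, with early switchers censored at the last one. Because that censoring may be informative, add a sensitivity analysis that counts the switch as an event.
3. **Response.** State that Step 1 best response ends at Step 2 start, which reconciles Sections 6.1.4.4 and 9.4.
4. **Q-TWiST.** End TOX1, TWiST1 and PFS1, and start TOX2 and TWiST2, at the earlier of first progression or Step 2 start. Assign EQ-5D visits to states by the same date. Moving only the end of the first-line states would not be enough, because the gap lies in the entry rules for TOX2 and TWiST2.

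**Cost.** This is SAP wording. Step 2 registration is recorded, and Section 3.2.3 requires disease evaluation within 4 weeks before it. The price is a smaller Arm D set for objective 2.2.5: of 100 patients, 80, 60 or 40 would remain if 20%, 40% or 60% switched early. At a 23% response rate the 95% half-width, 1.96 × √(0.23 × 0.77 / n), widens from 8.2 points at n = 100 to 9.2, 10.6 or 13.0.

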1.8 Dabrafenib and Trametinib Combination

Trametinib has been combined with dabrafenib in an effort to delay the development of resistance to dabrafenib and potentially reduce toxicity associated with BRAF inhibitor induction of paradoxical activation of the MAP kinase pathway in cells lacking a BRAF mutation.

A phase I/II study demonstrated the feasibility of combining full doses of dabrafenib (150 mg twice daily) and trametinib (2 mg daily). In the phase II component of the trial, 162 patients whose tumor contained a V600 mutation were randomly assigned to one of 3 regimens: dabrafenib (150 mg twice daily) as monotherapy, dabrafenib plus trametinib (150 mg twice daily and 1 mg once daily, respectively), or dabrafenib plus trametinib (150 mg twice daily and 2 mg once daily, respectively). In the analysis of this randomized component of the trial, treatment with the combination regimen using full doses of dabrafenib and trametinib (2 mg daily dose) significantly prolonged PFS compared to dabrafenib monotherapy (median 9.4 vs 5.8 months, HR 0.39, 95% CI 0.25-0.62) and significantly increased the proportion of patients alive and progression-free at one year (41% vs 9%).¹³ Recent updates for patients enrolled in the full dose dabrafenib + trametinib cohort showed a median overall survival of 25 months and a 2 year survival of 75% (56%-86%) for patients with a normal LDH compared with 18% (6%-36%) for patients with an elevated LDH.²⁵ Dermatologic toxicity, manifested by squamous cell carcinoma (including keratoacanthoma) was decreased in both the combination arms relative to dabrafenib alone (5% vs 19%), although the incidence of pyrexia was increased (71% vs 26%).

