1.9 Study rationale

Given these new treatment approaches for patients with BRAFV600 mutant melanoma, patients and physicians now (and in the future) have to make a choice regarding initial treatment and the sequence of these modalities. There is currently little information to guide this choice. While BRAFi therapy appears to

be equally active in patients whose disease has progressed following immunotherapy¹⁴ and those who are immunotherapy-naïve there is no formal data on its activity following resistance to ipilimumab + nivolumab. Similarly, there is no formal prospective data on the activity of ipilimumab (or even the feasibility of stopping BRAFi therapy and administering ipilimumab) following disease progression on BRAF (+/- MEK) inhibitor therapy. While some anecdotal data suggests that response to either nivolumab or the ipilimumab + nivolumab combination can be seen in patients whose disease has become resistant to BRAFi, there is no formal data to assess the activity, tolerability or feasibility of this promising immunotherapy combination in that setting. It is conceivable that patients treated initially with immunotherapy may get the benefit of durable response in a subset of patients (up to 40%-50%) without compromising the benefit of subsequent BRAF inhibitor therapy for those patients who exhibit disease progression, while those started on BRAF/MEK inhibitor therapy may not be able to benefit as much from subsequent immunotherapy at time of progression as they would in the treatment naïve setting. It is also possible that the high response rate and prolonged PFS associated with dabrafenib + trametinib combination relative to ipilimumab + nivolumab may overwhelm any benefit that might be achieved with initial immunotherapy. Further, it is possible that subsets of patients, defined by clinical and/or tumor characteristics (Performance Status, disease stage, serum LDH level, PTEN loss, immune infiltration, PDL1 expression, germ line polymorphisms, etc.), might do better with one initial therapy or sequence than with the other. Finally, the sequence of treatments may be influenced by Quality of Life factors that are largely unknown for either treatment approach as described below.

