 - 3.2.1.2 ([3.1.9](#)) - Only prior systemic therapy as part of Step 1 is allowed. Patients who received allowed systemic therapy in the adjuvant setting prior to Step 1 (see Section [3.1.9](#)) and were eligible for Step 1 are not excluded from proceeding to Step 2 if they meet other eligibility criteria.
 - 3.2.1.3 ([3.1.22](#) and [3.1.21](#)) malabsorption, swallowing difficulty, or other conditions that would interfere with the ingestion or absorption of dabrafenib or trametinib, or history of retinal vein occlusion are acceptable for patients crossing over to Arm D (ipilimumab + nivolumab) treatment.
 - 3.2.1.4 ([3.1.19](#), [3.1.22](#)) history of autoimmune disease, excluding interstitial lung disease or pneumonitis, is allowed in patients crossing over to Arm C (dabrafenib/trametinib) therapy (see [3.2.4](#)).
 - 3.2.1.5 ([3.1.10](#), [3.1.12](#)) Patients crossing over from Arm A (nivolumab/ipilimumab) to Arm C (dabrafenib/trametinib) who underwent surgery or SRS to CNS metastases need not be off of steroids to start treatment (see [3.2.6](#)).
 - 3.2.1.6 ([3.1.14](#)) There is no restriction on serum LDH at crossover.
 - 3.2.1.7 ([3.1.16](#)) Patients with a history of cardiovascular risks that developed during Step 1 of therapy should be discussed with study PI at time of crossover.
 - _____ 3.2.2 Patients randomized to Arm A on Step 1 must have melanoma that is metastatic and clearly progressive on Step 1 therapy prior to crossing over to Arm C.

NOTE: Patients should (if possible) be at least 1 week from documented PD on Step 1 of current study. All sites of disease must be evaluated within 4 weeks prior to registration.
 - 3.2.3 Patients randomized to Arm B on Step 1 may cross over to Arm D at or prior to disease progression

Rev. 6/16

Rev. 10/17

Rev. Add13

Rev. Add10
Rev. Add16

NOTE: If possible, patients should wait to cross over until after the cycle with the next protocol-required imaging assessment is completed. All sites of disease must be evaluated within 4 weeks prior to Step 2 registration.

NOTE: Patients should start Arm D treatment at least 1 week after stopping dabrafenib and trametinib, unless otherwise clinically indicated.

NOTE: Baseline labs and QOL assessments should be completed, and patients should follow the Arm D schedule as described in Section [5.1.4](#).

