9.1 Study Design and Objectives

In this randomized phase III study, patients with unresectable stage III or stage IV BRAFV600 mutant melanoma will be equally randomized to A: ipilimumab-nivolumab (with subsequent dabrafenib in combination with trametinib) or B: dabrafenib in combination with trametinib (with subsequent ipilimumab-nivolumab) using the stratification factors (ECOG PS, Serum LDH). The stratified randomization will be based on the permuted block method.

The primary objective is to evaluate whether initial treatment with either combination ipilimumab-nivolumab (with subsequent dabrafenib in combination with trametinib) or dabrafenib in combination with trametinib (with subsequent ipilimumab-nivolumab) significantly improves 2 year overall survival.

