9.4 Statistical Analysis Plan

The primary (2-year OS rate) and secondary efficacy (OS, 3-year OS rate) analyses will include all randomized patients (intent-to-treat analysis). Toxicity analysis will be based on all cases who received the treatment regardless of eligibility.

The primary endpoint, 2-year OS rate will be estimated (proportion of patients alive after 2 years of follow-up time) and will be compared between the two arms using the Mantel-Haenszel test (stratified by ECOG PS and LDH) based on two-sided overall type I error rate of 0.05 adjusting for two-interim analysis. Mantel-Haenszel test will compare the 2-year OS rates while controlling for the stratification factors. The difference in 2-year OS rates in arms A and B will be estimated and presented with 95% repeated confidence interval of Jennison-Turnbull. In addition, OS distribution will be estimated using the Kaplan-Meier method. The distribution of OS will be compared using the stratified log rank test. Hazard of OS will be estimated as a function of time in arm A and in arm B (as randomized in step 1 to arm A vs. B) and presented graphically.

In PFS distribution will be estimated using the Kaplan-Meier method.

PFS distributions will be compared using the log rank test and response rates will be compared using the Mantel-Haenszel test (stratified by ECOG PS and LDH) test in arms A vs. B. 3-year OS rate (proportion of patients alive after 3 years of follow-up) will be estimated by treatment arms and will be compared using the Mantel-Haenszel test (stratified by ECOG PS and LDH) in arms A vs. B. Cases censored before 3-year will not be included in this analysis, but this number is expected to be minimal.

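### The same-regimen comparisons A vs D and B vs C are non-randomised but planned with unadjusted tests, so a case-mix difference at crossover can appear as a loss or gain of drug activity, or mask one

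*Combined protocol and SAP*

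**What the plan says.** Objective 2.2.5 asks for the activity of ipilimumab + nivolumab after progression on dabrafenib + trametinib, "in comparison to its activity and safety in dabrafenib + trametinib naïve patients". Objective 2.2.4 is its mirror image. Section 1.9 gives the expected reading: patients who start on targeted therapy "may not be able to benefit as much from subsequent immunotherapy at time of progression as they would in the treatment naïve setting".

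For A vs D, Section 9.4 states: "Response rates will be compared using the Fisher's exact test and PFS will be compared using the log-rank test". It then adds: "Analyses specified in this paragraph will be repeated for arms B vs. C comparison". No stratification, covariate model, weighting or warning goes with either comparison.

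Randomisation applies only to A vs B, "using the stratification factors (ECOG PS, Serum LDH" (Section 9.1). Section 4.2 is headed as a randomisation, but it describes re-registration in which the Step 2 arm follows from the Step 1 arm. Arm C takes Arm A patients who have clearly progressed. Arm D takes Arm B patients at or before progression. Both must meet the Step 2 criteria in Section 3.2. On LDH, Section 3.2.1.6 says: "There is no restriction on serum LDH at crossover".

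By contrast, the randomised 2-year OS rate is "compared between the two arms using the Mantel-Haenszel test (stratified by ECOG PS and LDH"). The 3-year OS rate and A vs B response are stratified in the same way, and OS has a stratified log-rank test. A vs B PFS is given a log-rank test with no stratification mentioned.

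**The concern.** The question behind 2.2.4 and 2.2.5 is whether prior treatment with the other regimen changes activity. The formal nulls of the two tests are equal response probability and equal hazards. Reading a rejection as an effect of prior therapy also requires that the two groups would have had the same outcomes without it, and crossover gives no assurance of that.

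The protocol recognises the problem elsewhere. Section 1.2 discounts earlier retrospective sequencing data because of biases in who was chosen for which initial treatment. Section 5.9.1 urges caution about post-crossover comparisons, but only for patient-reported outcomes. Section 9.7 adjusts its non-randomised genetic survival analyses for LDH and performance status, among other factors. The A vs D and B vs C efficacy comparisons get none of this. The LDH and PS subset analyses in Section 9.4 are general, exploratory and not tied to these comparisons.

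At stake is what the trial will say about loss of benefit when a regimen is given second.

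**Working it through.** **Plan's own figure.** The documents give no sample size, power or alpha for A vs D or B vs C, so there is nothing to reproduce for this comparison. The primary A vs B figure does reproduce: 70% vs 50%, 90% power and two-sided 0.05 give 134 per arm with continuity correction, 268 in total against the stated 270.

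**Inputs from the documents.** Section 11.3 (Aim 2b) expects 150 first-line and 100 second-line ipilimumab/nivolumab patients. Section 1.8 reports 2-year OS on full-dose dabrafenib + trametinib of "75% (56%-86%) for patients with a normal LDH compared with 18% (6%-36%) for patients with an elevated LDH". Under proportional hazards the implied OS hazard ratio is ln(0.18)/ln(0.75) = 5.96. The extremes of the quoted intervals give ln(0.36)/ln(0.56) = 1.8 to ln(0.06)/ln(0.86) = 18.7. This shows that LDH is strongly prognostic. It is an OS figure for one regimen, so it is not used as a PFS input below.

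**Inputs not in the documents (assumed, shown as ranges).** Elevated-LDH share in each group; LDH hazard ratio for PFS; response rate by LDH; PFS median of about a year with 12 to 36 months of follow-up.

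**Mechanism.** Let the regimen work identically within each LDH stratum, and let q be the elevated-LDH share in a group. Then

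- PFS in a group: S(t) = (1 − q)·S_N(t) + q·S_N(t)^HR
- response in a group: p = (1 − q)·p_N + q·p_E

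If q differs between groups, S and p differ although prior therapy has done nothing.

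**PFS, 150 vs 100, two-sided 5%, no effect of prior therapy.**

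| Elevated LDH, first → second line | LDH HR | Unadjusted log-rank rejects | LDH-stratified rejects |
|---|---|---|---|
| 35% → 50% | 1.5 / 2 / 2.5 | 7.0% / 11.1% / 16.7% | 4.4-6.1% (range over all scenarios starting at 35%) |
| 35% → 65% | 1.5 / 2 / 2.5 | 12.9% / 29.2% / 46.2% | same range |
| 40% → 60% | 1.5 / 2 / 3 | 8.4% / 16.7% / 28.4% | 5.4% / 4.9% / 5.3% |
| 40% → 70% | 1.5 / 2 / 3 | 13.5% / 29.5% / 57.6% | 5.1% / 5.7% / 6.9% |
| 40% → 40% | 1.5 to 3 | 4.5-5.7% | not needed |

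The 35% rows use 3,000 simulated trials each with 24 months of follow-up. The 40% rows use 1,500 each with censoring uniform on 12 to 36 months. Repeating the shifted scenarios with a median of exactly 12 months moved no unadjusted entry by more than 1.5 percentage points.

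**Response, 150 vs 100.** Example with response 60% (normal LDH) and 35% (elevated):

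- first line, q = 0.35: 0.65 × 0.60 + 0.35 × 0.35 = 0.5125
- second line, q = 0.65: 0.35 × 0.60 + 0.65 × 0.35 = 0.4375

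Exact rejection rates for Fisher's test:

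| Response, normal / elevated LDH | 35% → 50% | 35% → 65% |
|---|---|---|
| 60% / 45% | 5.0% | 8.7% |
| 60% / 35% | 7.2% | 18.5% |
| 65% / 30% | 10.5% | 33.2% |

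With no shift Fisher's test rejects in 3.8-4.0%. Mantel-Haenszel stratified by LDH gives 4.8-5.2% throughout.

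**Opposite direction.** If the elevated-LDH share falls from 35% to 25% at crossover, Fisher's test rejects in 4.6-7.0% and the log-rank in 5.7-8.2%, with Arm D looking better.

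**Fewer crossovers.** Appendix XVI reports a lower crossover rate than anticipated. With an assumed 60 patients in Arm D, the highest rates in the scenarios starting at 35% are 27.0% (Fisher) and 36.0% (log-rank).

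**The case against.** The strongest reply is that these are secondary comparisons with no alpha, power or decision rule, and that an unadjusted description does answer how active the regimen was in the patients who received it second. That stands. It supports keeping the unadjusted result, not presenting it alone.

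A reader might infer that second-line activity will be biased downwards. The documents do not support a fixed direction. Patients entering C or D must have survived to crossover, must again have ECOG PS 0-1, and must have toxicity resolved to grade 1 or less. Some enter D before progression. All of this could make second-line patients look better. The absence of an LDH limit at crossover does not show a shift either, because Step 1 has no LDH limit.

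A reader might also infer that Section 9.4 stratifies every other efficacy test and omits only these. It does not: A vs B PFS is stated without stratification.

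On size, the LDH shares at crossover and the PFS and response differences by LDH are all assumed, and the lower end of the range is close to nominal.

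On the remedy, LDH and PS at Step 2 registration are measured after Step 1 therapy and may partly be its consequence. Adjusting for them can remove part of the effect being studied. This stands too, and it is why the adjusted analysis should sit beside the unadjusted one and not replace it.

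**Conclusion.** The point holds as a modest, inexpensive improvement to secondary analyses. Section 9.4 plans unadjusted tests for groups that randomisation did not form, and nothing elsewhere in the documents supplies adjustment or a caveat for these efficacy comparisons. A difference in LDH or PS at the start of the regimen can show up as changed drug activity, in either direction, or conceal a real change.

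The size cannot be derived from the documents. The rejection rates of about 7-58% (log-rank) and 5-33% (Fisher) hold only for the assumed rises in elevated LDH and the assumed LDH effects. Where the shift is small or LDH is weakly prognostic, the inflation is slight. The primary 2-year OS comparison is randomised and stratified, and is not touched.

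**What to change.** In Section 9.4, for A vs D and B vs C:

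- State that the comparisons are non-randomised.
- Tabulate LDH, ECOG PS and progression status at the start of each regimen.
- Beside the unadjusted results, add a stratified log-rank test with an adjusted Cox hazard ratio for PFS, and a stratified Mantel-Haenszel difference for response, each with a 95% CI. Use LDH and PS at randomisation for A and B, and at Step 2 registration for C and D.
- Base any statement about changed drug activity on both sets of results.
- Show progressed and pre-progression entrants to Arm D separately.

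The cost is SAP wording and a few extra tables. The schedule in Section 7.1.1 already collects ECOG PS and chemistry including LDH at baseline and at crossover. Two limits should be written into the plan: unmeasured confounding remains, and adjustment for values at crossover may remove part of the effect of Step 1 therapy.
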